7.7.1 Adverse Events

Treatment emergent AEs (TEAEs) are defined as follows:

- TEAEs (the double-blind treatment phase): Events with start date on or after the date of initial application of study drug in the double-blind treatment phase, and up to 17 days after the date of final application of study drug in the double-blind treatment phase and before the first application of DSP-5423P in the open-label treatment phase.
- TEAEs (DSP-5423P treatment period): Events with start date on or after the date of initial application of DSP-5423P either in the double-blind treatment period for 40MG and 80MG groups or in the open-label treatment period for placebo group and up to 17 days after the date of final application date of DSP-5423P.

AE with missing or incomplete start date after imputation will be considered as TEAE.

Treatment-related TEAE:

A treatment-related TEAE is defined as a TEAE for which the causal relationship to the study treatment is either 'definite', 'probable', or 'possible'.

Common TEAE:

Common TEAE in the double-blind treatment phase are PT of TEAEs experienced by 2% or more subjects in 40MG or 80MG group in the safety population.

Common TEAE in the DSP-5423P treatment period are PT of TEAEs experienced by 2% or more subjects in the overall-to-FLEX DOSE group in the DSP-5423P dosed population.

The summary of AEs will be limited to treatment-emergent AEs (TEAEs). The number and percentage of subjects with TEAEs during the double-blind treatment phase on the safety population and DSP-5423P treatment period on the DSP-5423P dosed population will be summarized by preferred term, system organ class, and treatment group. Summaries will be repeated by country and race.

Specifically, this will cover the following items:

- any TEAE;
- TEAE leading to death;
- TEAE leading to treatment discontinuation;
- serious TEAE;

- extrapyramidal TEAE;
- skin-related TEAE;
- treatment-related TEAE;
- treatment-related TEAE leading to death;
- treatment-related TEAE leading to treatment discontinuation;
- treatment-related serious TEAE;
- treatment-related extrapyramidal TEAE;
- treatment-related skin-related TEAE;

Skin-related TEAE is defined as the TEAE occurred at the application site (recoded in the CRF) and identified as TEAE with a wording “Application site” in MedDRA LLT.

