The number and percentage of subjects reporting each TEAE will be summarized by system organ class (SOC) and preferred term (PT) for the double-blind treatment phase on the safety population and for the DSP-5423P treatment period on the DSP-5423P dosed population. Whenever appropriate, SOCs are sorted by alphabetically and PTs are sorted within SOC in descending order of frequency of the active group for the double-blind treatment phase and the Overall-to-FLEX DOSE group for the DSP-5423P treatment period. If there are ties, PTs are sorted by alphabetically. The following summaries will be produced for the double-blind treatment phase and DSP-5423P treatment period:

- TEAE by SOC and PT*;
- Common TEAE by PT#;
- treatment-related TEAE by SOC and PT;
- TEAE by maximum severity and PT;
 - This will be repeated for extrapyramidal TEAE and skin related TEAE
- TEAE leading to treatment discontinuation by SOC and PT+;
- Serious TEAE by SOC and PT;
- extrapyramidal TEAE by PT#+;
- skin related TEAE by PT#+;
- skin related TEAE by PT and application site;

Statistical Analysis Plan

Version: 2

Study No. D4904020

- TEAEs by first onset (Day 1 to 7, Day 8 to 14, Day 15 to 28, Day 29 or later), SOC and PT in the double-blind treatment phase;
 - This will be repeated for extrapyramidal TEAE and skin related TEAE
 - TEAEs by first onset (Week 1 to 6, 1 to 13, 14 to 26, 27 to 39, 40 to 52, 53 or later, Week 1=Day 1 to 7, Week 2=Day 8 to 14), SOC and PT in the DSP-5423P treatment period;
 - This will be repeated for extrapyramidal TEAE and skin related TEAE
 - TEAEs by DSP-5423P dose at onset (40MG, 60MG, 80MG), SOC and PT in the DSP-5423P treatment period;
 - TEAEs by modal daily dose (40MG, 60MG, 80MG), SOC and PT in the DSP-5423P treatment period;
 - TEAEs leading to dose reduced by SOC and PT in the DSP-5423P treatment period+;
 - TEAEs leading to dose increased by SOC and PT in the DSP-5423P treatment period+;
- * Summaries will be repeated by country and race. # Summaries will be repeated by country. +: listing will be produced.

In the above summaries, unless otherwise specified, if a subject experienced more than one episode of a TEAE within a PT or a SOC, the subject is counted only once in the PT or the SOC.

For summaries based on DSP-5423P treatment period and on-going event carried from DB phase, the following items will be handled as described. No handling will be applied for items not listed below;

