- Serious TEAE: if the event is flagged as serious at least one time throughout DSP-5423P treatment period, the event will be summarized as Serious TEAE.
- Causality: Causality will be prioritized as listed in order, "DEFINITE", "PROBABLE", "POSSIBLE" and "NOT RELATED" in on-going event.
- Severity: Severity will be prioritized as listed in order, "SEVERE", "MODERATE", "POSSIBLE", "MILD" in on-going event.

Statistical Analysis Plan

Version: 2

Study No. D4904020

- Event leading to Dose Reduced: for on-going event, if the event is flagged as dose reduced in action taken at least one time throughout DSP-5423P treatment period, the event will be summarized as event concerned.
- Event leading to Dose Increased: for on-going event, if the event is flagged as dose increased in action taken, at least one time throughout DSP-5423P treatment period, the event will be summarized as event concerned.
- Application site: if on-going event have multiple application site throughout DSP-5423P treatment period, application site will not be prioritized, and the event will be counted per application site within associate PT.

For the summaries by maximum severity, if a subject experienced more than one episode of a TEAE within a PT, the subject is counted only once in the PT at the maximum severity. In determining maximum severity, severities are ranked from missing (not specified), mild, moderate, to severe. If the maximum severity is missing, the episode will be displayed as 'not specified'.

For the summaries of skin-related adverse events, if a subject experienced more than one episode of a TEAE within a PT for an application site of study drug, the subject is counted only once in the PT for the application site. If a subject had a PT occurred at different application sites, it will be counted per application site within associate PT.

For the summaries by first onset, if a subject experienced more than one episode of an TEAE within a PT, the subject is counted only once in the PT for the first episode. Denominator of percentage for each period of interest is the number of subjects who were treated with the study medication regardless of any suspensions of study medication between the initial and final date of application of study drug.

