For the summaries by DSP-5423P dose at onset, if a subject experienced more than one episode of an TEAE within a PT, the subject is counted only once in the PT by DSP-5423P dose at onset. For example, if a subject has same PT twice but onset dose for each is not same, these PTs will appear one time each in different dose categories. Denominator of percentage for each dose is the number of subjects who have experienced the dose of interest at least once in the DSP-5423P treatment period in case that no DSP-5423P dose at onset is available, for example, the onset date is middle of prescribed periods or the onset date is after the final application, DSP-5423P dose at onset will be set to last non-missing dose taken at prior to the onset date.

No statistical comparisons of AEs between treatment groups will be performed.

Narrative of Serious AE will be produced by a subject who experienced SAE.

Hospitalization record will be listed.

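### The first-onset adverse event tables count events up to 17 days after the last patch but, on the natural reading, divide by subjects still on treatment in the period, so later-period percentages are modestly overstated

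*SAP*

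**What the plan says.** All the rules are in SAP 7.7.1.

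- **Numerator.** A double-blind TEAE starts on or after the first double-blind application and "up to 17 days after the date of final application of study drug in the double-blind treatment phase", and before the first open-label patch. For the DSP-5423P treatment period the window runs "up to 17 days after the date of final application date of DSP-5423P".
- **Counting.** In the first-onset tables, "the subject is counted only once in the PT for the first episode".
- **Periods.** Double-blind: "TEAEs by first onset (Day 1 to 7, Day 8 to 14, Day 15 to 28, Day 29 or later". DSP-5423P treatment period: "TEAEs by first onset (Week 1 to 6, 1 to 13, 14 to 26, 27 to 39, 40 to 52, 53 or later". Both tables are repeated for extrapyramidal and skin-related events.
- **Denominator.** "Denominator of percentage for each period of interest is the number of subjects who were treated with the study medication", and this applies "regardless of any suspensions of study medication between the initial and final date of application of study drug".
- **Neighbouring table.** The dose-at-onset summary has a rule for late onsets: if "the onset date is after the final application, DSP-5423P dose at onset will be set to last non-missing dose". The first-onset summary has no such rule.

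**The concern.** The numerator has a 17-day tail after the last patch and the denominator does not. A subject with a last patch on Day 14 and a first onset on Day 20 has a valid TEAE in 'Day 15 to 28'. That subject was not treated in the period and so is not in its denominator.

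The mismatch is zero in a period that starts on Day 1 and upward in every other period. Early discontinuers drive it, so it can differ between arms if dropout differs. The tables describe when extrapyramidal and application-site events first appear, and long-term safety is a stated secondary objective (Protocol 5.2).

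**Working it through.** The documents give no percentages for these tables, so there is no figure to reproduce. The check is set logic followed by an illustration.

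**Set logic.** Let s be the day of the last patch and a the first day of a period. The subject is in the denominator if s ≥ a. The subject can be in the numerator if s + 17 ≥ a. Subjects with a − 17 ≤ s < a can therefore be in the numerator only. In the double-blind table this affects every period after 'Day 1 to 7'. In the DSP-5423P table, 'Week 1 to 6' and 'Week 1 to 13' both start on Day 1, so the first affected period is 'Week 14 to 26'. Completers who enter the open-label phase add nothing to the double-blind mismatch, because their window closes at the first open-label patch.

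**Double-blind illustration.** From the documents: 167 randomized and 133 required per arm (Protocol 15.1), which implies dropout of 34/167 = 20.4%. Adverse events are collected until the follow-up visit (Protocol 12.1.1 and 12.3), which falls 6 to 17 days after the last application (Protocol Tables 4 and 5, footnote g). Assumed: discontinuers' last patch even over Days 1-41; completers' window closing at Day 42; on-treatment hazard 0.10/42 per day; post-treatment hazard 1, 2 or 3 times that.

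Overstatement = (all counted events ÷ counted events among subjects in the denominator) − 1:

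| Period | Full 17-day tail (1×/2×/3×) | Collection ends at a visit even over days 6-17 (1×/2×/3×) |
|---|---|---|
| Day 1-7 | 0% | 0% |
| Day 15-28 | 5.4 / 10.2 / 14.4% | 2.9 / 5.6 / 8.0% |
| Day 29 or later | 6.0 / 10.8 / 14.8% | 3.2 / 5.8 / 8.2% |

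In absolute terms, the smallest 'Day 29 or later' figure (3.2%) is 3.24% reported against 3.14% matched.

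The other comparator extends the denominator to everyone whose 17-day window reaches the period. With 20% dropout and a full tail, about 144 subjects are in the 'Day 29 or later' denominator and about 14 more could contribute events. The overstatement is then 14/144, about 10%. It is about 4% at 10% dropout and 16% at 30%.

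**'Week 53 or later', placebo-to-flexible-dose.** The period starts on on-treatment Day 52 × 7 + 1 = 365. Planned open-label treatment in Japan is 52 weeks, to Day 364, and the Visit 112 window is Days 351-379 (Protocol Table 5). A subject who stops exactly on Day 364 is outside the denominator but has a TEAE window to Day 364 + 17 = 381.

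Assume last patches even over Days 351-379 (29 days), a full tail and a constant hazard. A subject with last patch on day s has s + 17 − 364 = s − 347 days at risk within the period.

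- s = 351 to 364: 4 + 5 + … + 17 = 147 days, outside the denominator.
- s = 365 to 379: 18 + 19 + … + 32 = 375 days, inside it.
- Against a numerator restricted to subjects in the denominator: (147 + 375)/375 = 522/375 = 1.39. With collection ending evenly over days 6-17 this is 1.26.
- Against an extended denominator: 29/15 = 1.93.

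The cell is small. Japanese sites in SAP Appendix II sum to 164 randomized, about 55 on placebo at 1:1:1 before any dropout.

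**The case against.** **The denominator sentence never says 'treated in that period'.** If it means all treated subjects, the mismatch disappears. But the words tying the denominator to each period, and the clause on suspensions, would then have no purpose. The per-period reading is the natural one, and the sentence needs clarifying either way.

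**Seventeen days is the outer limit of the tail.** Collection stops at a follow-up visit that may be as early as day 6. This stands, and it roughly halves the double-blind figures.

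**A reader might infer a false late rise in onset.** The documents do not support that. In the illustration the overstatement is nearly flat after the first week (2.9% against 3.2% at equal hazard in the last two columns). The periods differ in length, so their percentages are not comparable rates. The denominator also keeps subjects who have already had their first episode, which pulls late percentages down. 'Overstated' therefore means relative to a matched numerator and denominator, not to the true onset risk.

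**A reader might take these as the only displays of timing.** They are not. The SAP plans listings of extrapyramidal and skin-related events, DIEPSS by visit (7.7.2), skin irritation by visit (7.7.4) and antiparkinson drug use by treatment interval (7.4.3).

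**A reader might suppose that every Japanese placebo-first completer feeds the Week 53 numerator.** A subject with last patch on Day 351 and follow-up 6 to 13 days later finishes event collection by Day 364. The problem also does not carry over to Japanese subjects first randomized to 40 or 80 mg. They are scheduled to Week 58 (SAP 6.3 B), so they are properly in that denominator.

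**Conclusion.** The mismatch follows from the SAP's own definitions, given the natural reading of the denominator sentence. In the double-blind 'Day 29 or later' column its likely size is about 3-8% relative with a realistic end of collection, and 6-15% with a full tail. Both ranges rest on assumed 20% even dropout and post-treatment hazards of 1 to 3 times the on-treatment hazard.

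'Week 53 or later' for placebo-to-flexible-dose is the one column where the distortion could be large: about 1.4 times against a restricted numerator and 1.9 times against an extended denominator, with even last patches and a full tail. The 1.9 should not be quoted alone, because it is a head-count ratio and not the measure in the double-blind table above. A percentage above 100% is arithmetically possible in a near-empty cell, but nothing in the documents shows that it would occur.

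The tables are descriptive: SAP 7.7.1 rules out statistical comparison of adverse events. The main summaries by system organ class and preferred term use whole populations as denominators and are unaffected, as is every tested result. Severity: minor.

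**What to change.** In the first-onset paragraph of SAP 7.7.1, use one window for both parts. Either:

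- **A.** Put a subject in a period's denominator if the period overlaps the interval from initial application to final application + 17 days, ended by the first open-label patch for the double-blind tables; or
- **B.** Limit the by-onset numerators to onsets on or before the final application, and show post-treatment onsets in a separate row.

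B has the advantage of making off-drug onset visible. It also moves out the tail events of subjects who are in the denominator, so it measures on-treatment onset only, and the 1.39 ratio above is not its comparator. Whichever is chosen, state explicitly that the denominator is specific to the period.

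Cost: one sentence and one changed derivation, with no new data.

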#### 10.1.3 The Open-label Treatment Phase

DSP-5423P 20 mg patches and DSP-5423P 40 mg patches will be used in the open-label treatment phase.

One or two patches of DSP-5423P will be applied once daily to the eligible subjects (Section 8.3 Criteria before the open-label treatment phase, p32) for a further 28 weeks (outside Japan) or 52 weeks (in Japan). The initial dose of DSP-5423P in the open-label treatment phase will be 40 mg/day. After DSP-5423P 40 mg/day

application after Visit 6 until Visit 101, DSP-5423P will be applied as flexible dose within a range from 40 mg/day to 80 mg/day according to the dose adjustment criteria (Section 10.2 Dose Adjustment Criteria in the open-label treatment phase). Table 9 shows the combinations of the patches in the open-label treatment phase.

**Table 9 The study drug patches to be applied  
in the open-label treatment phase**

Treatment	The study drug	Number of patches
DSP-5423P 40 mg/day	A	1
DSP-5423P 60 mg/day	A, B	2
DSP-5423P 80 mg/day	A, A	2

A, DSP-5423P 40 mg patch; B, DSP-5423P 20 mg patch

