## 10.2 Dose Adjustment Criteria in the open-label treatment phase

In the open-label treatment phase, the DSP-5423P dose can be increased or reduced by 20 mg/day at each adjustment within a range of 40 to 80 mg/day according to the following dose adjustment criteria.

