### At scheduled visit

- When the CGI-S score is between 4 and 7 and when no safety concerns arise, the DSP-5423P dose should be increased.
- When the CGI-S score is 3 or lower with no safety concerns and when the Investigator expects further efficacy of DSP-5423P, the DSP-5423P dose can be increased.

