Modal daily dose will be calculated only for the open-label treatment phase and DSP-5423P treatment period:

- Modal daily dose is the most frequently prescribed daily dose during the treatment phase. In the case where there is more than one most frequent dose, eg, both 40 and 60 mg/day are equally frequent then the maximum dose level (eg, 60 mg/day) will be the modal daily dose.
- Modal daily dose will be presented as the number and percentage of subjects for the following categories: 40 mg, 60 mg, 80 mg and Missing

Last daily dose

Last daily dose will be calculated and summarized in summary statistics only for the open-label treatment phase and DSP-5423P treatment period:

- Last daily dose is the prescribed daily dose at the final prescription for the subject during the treatment phase.
- Last daily dose will be presented as the number and percentage of subjects for the following categories: 40 mg, 60 mg, 80 mg and Missing

Maximum dose

Maximum dose will be presented only for the open-label treatment phase and DSP-5423P treatment period:

- Maximum dose is the prescribed daily dose throughout the treatment phase.
- Maximum dose will be presented as the number and percentage of subjects for the following categories: 40 mg, 60 mg, 80 mg and Missing

Cumulative dose

Cumulative dose will be calculated and summarized in summary statistics only for the open-label treatment phase and DSP-5423P treatment period:

- Cumulative dose is Sum of prescribed daily dose x duration of each prescription (days)

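### The adverse-event tables by dose at onset and by modal dose ignore time spent at each dose, so equal true risk prints as different percentages by dose, in a direction the documents do not fix.

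*SAP*

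**What the plan says.** SAP 7.7.1 plans two TEAE tables by dose over the DSP-5423P treatment period.

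- **Dose at onset.** A subject counts once per preferred term at each dose where an episode began. The denominator rule is "Denominator of percentage for each dose is the number of subjects who have experienced the dose of interest at least once". An event with no dose on its onset date, including one after the final application, goes to the last earlier dose.
- **Modal dose.** The entry is "TEAEs by modal daily dose (40MG, 60MG, 80MG), SOC and PT in the DSP-5423P treatment period". SAP 7.5.1 defines the classification: "Modal daily dose is the most frequently prescribed daily dose during the treatment phase". If two doses "are equally frequent then the maximum dose level (eg, 60 mg/day) will be the modal daily dose".

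No rate per unit of exposure is specified. SAP 7.5.1 summarises duration and mean, modal, last, maximum and cumulative dose, but not the time spent at each dose.

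The dosing rules are in the protocol. Section 10.1.3: "The initial dose of DSP-5423P in the open-label treatment phase will be 40 mg/day", and this lasts until Visit 101. Section 10.2: "the DSP-5423P dose can be increased or reduced by 20 mg/day at each adjustment within a range of 40 to 80 mg/day", with at least a week, in principle, between changes. At a scheduled visit: "When the CGI-S score is between 4 and 7 and when no safety concerns arise, the DSP-5423P dose should be increased". At CGI-S 3 or lower an increase is optional: "when the Investigator expects further efficacy of DSP-5423P, the DSP-5423P dose can be increased". Reductions for adverse events are allowed. The open-label phase lasts 28 weeks outside Japan and 52 weeks in Japan.

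For subjects randomised to 40 or 80 mg, the DSP-5423P treatment period begins on Day 1 of the double-blind phase (SAP 6.2). It therefore includes up to six weeks at a fixed dose. For the placebo arm it begins in the open-label phase.

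**The concern.** A percentage with everyone ever exposed as its denominator grows with time at risk. Here time at risk differs systematically by dose: in the open-label phase 40 mg comes first, 60 mg is a step on the way, and 80 mg can be reached only later. Columns headed 40, 60 and 80 mg invite a comparison by dose, yet with no dose effect at all they will differ.

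The modal-dose table has a second problem: it classifies a subject by dosing that happens after the event. Someone who stops early is classified on a few weeks of treatment, whereas someone who stays may end up under a dose reached months later.

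Long-term safety is a secondary objective, and these are the only planned adverse-event tables split by current or modal dose over the long-term period. The randomised tables cover six weeks and have no 60 mg arm. A reader cannot correct the percentages, because time at each dose is not reported.

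**Working it through.** The documents give no figure for these tables, so there is none to reproduce. The check asks what the tables print when risk is identical at every dose.

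**Inputs from the documents.** Open-label start at 40 mg/day until Visit 101 (taken as 7 days); steps of 20 mg; at least 7 days per step; open-label length 196 or 364 days; 42 double-blind days at 40 or 80 mg in the active arms; allocation 1:1:1.

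**Assumptions, not in the documents.** Constant hazard with 20% risk per 28 weeks (range 5% to 30%). In the simulation: the share escalating at each step, 4-week steps, 20% double-blind dropout, 30% open-label dropout per 28 weeks, and 28% of subjects in Japan (164 of 582, added up from SAP Appendix II). Modal dose is counted in days.

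**Step 1: closed form, fastest path, 28-week completers.**
λ = −ln(0.8)/196 = 0.001138 per day. Printed percentage at a dose = 1 − exp(−λ × days at that dose).

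| Arm | Days at 40/60/80 | Printed % at 40/60/80 |
|---|---|---|
| Placebo, then open label | 7/7/182 | 0.8/0.8/18.7 |
| 40 mg | 49/7/182 | 5.4/0.8/18.7 |
| 80 mg | 7/7/224 | 0.8/0.8/22.5 |
| Pooled (mean of arms) | – | 2.3/0.8/20.0 |

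The ratio of 80 to 40 mg is 20.0/2.3, or between 8 and 9, and 60 mg prints lowest. Over 52 weeks the pooled figures are 2.3/0.8/33.9. For 28-week completers they run from 0.6/0.2/5.0 at 5% risk to 3.7/1.3/30.0 at 30% risk.

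**Step 2: simulation with dropout** (300,000 subjects, same 20% risk, SAP counting rules).

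| Escalation | Mean days at 40/60/80 among those ever on the dose | Printed % at 40/60/80 |
|---|---|---|
| Everyone, fastest path | 21/7/183 | 2.4/0.8/18.2 |
| 75% per step, 4-week steps | 78/64/125 | 8.0/6.7/12.7 |
| 50% per step, 4-week steps | 116/100/90 | 11.7/10.3/9.4 |
| 25% per step, 4-week steps | 155/138/54 | 15.5/13.9/5.7 |

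The percentages follow the days. In the last row, 1 − exp(−λ × 155) = 16.2% and 1 − exp(−λ × 54) = 6.0%, close to the simulated 15.5 and 5.7; spread in individual durations lowers the simulated values slightly.

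**Step 3: modal dose, same scenarios in the same order.** Printed percentages at 40/60/80: 3.9/1.6/21.0, 15.4/22.6/20.2, 18.4/23.6/17.2 and 19.8/23.8/10.0. Among subjects with 42 or fewer active days, those classified under 40 mg are all of the 40 mg arm, none of the 80 mg arm (all fall under 80) and 33% to 100% of the former placebo arm, depending on titration speed; over all arms the share is 48% to 57%. On the fastest path a 40 mg-arm subject stays modal 40 until about open-label day 63, when 49 days at 40 mg are matched by 49 days at 80 mg and the tie goes to 80.

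**Step 4: does person-time repair it?** With first onsets per 100 patient-years at the dose, the constant-risk case prints flat: 42.0/42.1/41.5 on the fastest path and 41.5/41.7/41.9 with 50% escalating, against a true λ × 365.25 × 100 = 41.6. If the hazard is high early but still equal at every dose, one fastest-path simulation prints about 140/80/23 per 100 patient-years. Crude rates then show a false inverse gradient, so time since first active application must be handled as well.

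**The case against.** A reader might infer that the dose-at-onset table always makes 80 mg look dangerous. The documents do not support that. The order 40, 60, 80 is fixed in the open-label phase, but escalation is not forced: it is conditional at CGI-S 4 to 7, optional below that, and reversible. The double-blind weeks also count. At 10% risk per 28 weeks, open-label time alone gives 0.4/0.4/9.3 on the fastest path; with the double-blind weeks the pooled figures are about 1.1/0.4/10.0. At 50% escalation the table is nearly flat, and at 25% it reverses.

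Nor are early stoppers in general classified under 40 mg, since those in the 80 mg arm fall under 80. An extreme contrast can be produced for former placebo subjects by letting everyone titrate on schedule and stop only for adverse events: at 0.5% per week, 100% of modal-40 subjects have the event against 11.8% of modal-80 subjects. But modal 40 then contains only stoppers by construction, about 1 − exp(−0.005 × 2) = 1% of subjects.

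The safeguards are real. The SAP plans no statistical comparison of adverse events between groups. The randomised 40 mg, 80 mg and placebo tables give the unconfounded six-week comparison, and there are tables by onset window. Nothing in the documents draws a dose-response or labelling conclusion from the tables at issue.

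All of this limits the importance of the point without removing it. A descriptive table can still mislead, and showing results by randomised arm would not cure it, as the arm rows in Step 1 show.

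**Conclusion.** The point holds as a minor improvement. Neither table accounts for time at each dose, and the dosing rules tie dose to time on treatment, so the printed percentages generally differ by dose even when risk does not. Direction and size cannot be predicted: with equal risk, 80 mg can print between 8 and 9 times 40 mg (everyone on the fastest path) or little more than a third of it (5.7 against 15.5, a quarter escalating). The modal-dose table also depends on dosing after the event.

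These sizes rest on an assumed constant hazard, on assumed dropout and on assumed escalation shares; dose reductions were not among the factors varied. That time at dose is left out of both tables needs none of these assumptions. The primary analysis is unaffected.

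**What to change.** In SAP 7.7.1:

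1. Keep the percentages in the dose-at-onset table. Beside them show patient-years at each dose and subjects with first onset at that dose per patient-year, split by time since first active application, and by randomised arm where numbers allow. Define patient-years to match the numerator, which credits events up to 17 days after the final application to the last dose.
2. Footnote the dose-at-onset and modal-dose tables as unsuitable for comparing doses.
3. State that any adverse-event dose-response statement on 40 against 80 mg rests on the randomised double-blind tables.

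The cost is SAP wording and some extra derivation; prescription periods are already used in SAP 7.5 and 7.5.1. Some cells will be sparse, particularly once split by time window and arm, and the rates still assume a roughly constant hazard within each window.
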